#### Analysis of 6MWD at 12 months

To compare the effect of sustained delivery of 4 vs. 8 doses of the cell therapy product on 6MWD at 12 months (secondary objective 1), the regression model will include repeated measures up to 12 months and be used to estimate the adjusted least square mean difference between Arm 2 and Arm 3 at 12 months, together with 95% confidence interval. Additional pairwise comparisons of least square mean differences at 7, 8, 9 and 10 months will be conducted.

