Appendix H – Study Product Delivery Protocol

Delivery of the study product to participants will take place at the following visits: Months 0-3 and Months 6-9.

This protocol describes the general requirements for the study product delivery. Specific procedures to be followed are detailed in the SAPPHIRE **Study Product Delivery SOP**.

General Requirements:

- 1. Delivery of the study product (with associated procedures and post-delivery monitoring) must be the final study procedure/assessment performed during the study visit window.
- 2. Delivery of the study product must take place in an outpatient setting with access to full resuscitation measures, including a "crash cart" and "code blue" team.
- 3. Antihistamines and corticosteroids must be available for treatment of immune reactions should the need arise.
- 4. The study product will be injected by hand at a rate of no more than 2ml/minute only by the Principal Investigator or a delegated co-investigator.
- 5. The study product will be delivered through a peripheral IV cannula (20 gauge or larger).
- 6. Participants will be monitored for a minimum of 1 hour post product delivery. HR, BP, and oximetry will be measured every 15 minutes during this time period.
- 7. Discharge from the clinic must be approved by the Principal Investigator or delegated coinvestigator once the participant is judged to be clinically stable.

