**Figure 1: The SAPPHIRE 3-Arm trial design.**

**Rationale for the 3-arm trial design:** The SAPPHIRE trial is designed to maximize the generation of relevant results to inform further development or application of the cell therapy approach. The rationale for the main elements of the study is summarized below.

- **Course 1:** The first 6 months of the study has a standard design with 2:1 randomization to study product or placebo:
  - Arm 1: Participants will receive 4 monthly placebo injections.
  - Arms 2 and 3: Participants will receive 4 monthly injections of the cell therapy product.

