## 2.3 Sample Size

A total sample size of 39 participants (13 per arm) in an analysis of covariance using a planned comparison between the average of the two treatment arms versus control achieves 80% power to detect a minimally important mean difference of **50 meters** in the primary outcome (6MWD) using an F-test with a two-sided 5% significance level. The SAS procedure GLMPOWER was used to conduct the calculation (SAS Institute Inc. 2008. SAS/STAT® 9.2. User’s Guide. Cary, NC: SAS Institute Inc). The common standard deviation is assumed to be 85 and the correlation between baseline and 6 months is 0.80. These estimates are similar to those observed in our PHACeT trial where the standard deviation was 80 meters and the correlation between baseline and 6 month was 0.86. To account for 10% potential attrition, we will enroll and randomize 45 subjects (15 allocated to each arm).

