## 2.4 Framework

This will be a superiority trial, with primary aim to determine whether receiving a course of 4 monthly doses of eNOS-EPCs will improve the 6 minute walk distance (6MWD) at 6 months

compared to placebo. A minimally important mean difference of 50 meters was considered for this hypothesis.

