#### Analysis of Primary Outcome (6MWD at 6 months)

The primary analysis of our primary outcome, 6MWD assessed at baseline, one, two, three, four and six months, will use a general linear model with time (coded as a categorical variable) and group by time interaction as fixed covariates. As recommended for efficient analyses of longitudinal randomized controlled trials, baseline differences between the arms will be constrained through exclusion of the main effect for group. In addition to providing the unadjusted effect, we will adjust our estimate for the stratification factors (6MWD  $\leq 300$ m vs.  $> 300$ m and scleroderma APAH vs. all other eligible PAH categories), as well as age, gender and

baseline medication use (PDEVi and sGC stimulators vs. all other PAH-specific medications). The model will be estimated using Restricted Maximum Likelihood (REML), and degrees of freedom will be computed using the Kenward-Roger approach. Suitable covariance structures to account for correlation among repeated measures over time will be identified using likelihood ratio tests and information criteria (AIC and BIC). For the primary endpoint, the adjusted least square mean difference between the average of the two active treatment arms (Arms 2 and 3) versus placebo (Arm 1) at 6 months, together with 95% confidence interval, will be obtained and assessed at the two-sided 5% level of significance. Additional exploratory pairwise comparisons of least square mean differences at one, two, three, and four months will be conducted.

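### The Month 12 comparison of Arm 3 with Arm 2 makes no use of the arms' identical treatment up to the pre-dose Month 6 visit, and so gives up precision on a secondary objective

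*SAP*

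**What the plan says.** **Design.** SAP 2.1 states for Course 1: "Arms 2 and 3: Participants will receive 4 monthly injections of the cell therapy product". The two arms part only in Course 2, when Arm 2 switches to placebo and Arm 3 has a second course of cells. Allocation is randomised and the blind is to hold for all 12 months. Protocol 7.4 lists the Month 6 walk among the pre-treatment procedures, and Protocol Appendix H says that delivery of study product "must be the final study procedure/assessment performed during the study visit window".

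**Model.** SAP 5.2 (Analysis of Primary Outcome) and Protocol 11.4 use categorical time and a group-by-time interaction, and drop the group main effect so that the arms share one baseline mean. The primary contrast averages Arms 2 and 3 against Arm 1, so these are separate groups with their own mean at each post-baseline visit. The covariance structure is to be chosen from the data.

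**Month 12.** SAP 5.2 (Analysis of 6MWD at 12 months) and Protocol 11.5 extend this model to 12 months, to "be used to estimate the adjusted least square mean difference between Arm 2 and Arm 3 at 12 months". No further equality between the arms is named. Continuous secondary outcomes are to be analysed in a similar way, which covers objectives 5 (PVR) and 9 (SF-36).

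**Earlier visits.** "Additional exploratory pairwise comparisons of least square mean differences at one, two, three, and four months will be conducted"

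**The concern.** The plan constrains the baseline means for the sake of efficiency, because randomisation makes them equal. For Arm 3 against Arm 2 the same argument reaches further: the arms do not diverge until after the Month 6 assessments, so the walks at Months 1, 2, 3, 4 and 6 also precede any difference in treatment. Giving the two arms free means at those visits prevents the walks from acting as covariates. Having the data in the model does not cure this. With complete data and arm-specific means, the estimate is adjusted for the Month 0 walk alone.

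At stake is the precision of the randomised comparisons that isolate a second course (objectives 1, 5 and 9), with 15 randomised per arm and about 13 expected to be evaluable.

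**Working it through.** **Inputs.** From SAP 2.3: "The common standard deviation is assumed to be 85 and the correlation between baseline and 6 months is 0.80"; 13 evaluable and 15 randomised per arm; 50 m; two-sided 5%. The documents give no correlation with Month 12, so every such value below is an assumption.

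**1. The plan's own figure.** Residual SD = 85 × √(1 − 0.80²) = 51 m. Contrast variance = 51² × (1/13 + 1/26) = 300.1, so SE = 17.3 m. The F-test with 1 and 35 df gives 80.1% power for 50 m, against 80% stated. Attrition: 39/0.9 = 43.3, so 44, then 45 for three equal arms. The figures reproduce. No power is stated for Arm 3 against Arm 2.

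**2. Month 12 contrast, covariance known, complete data.** Variance = (2/n) × 85² × (1 − R²). R² comes from baseline alone under the SAP model, and from all six walks (Months 0, 1, 2, 3, 4, 6) if the Arm 2 and Arm 3 means are equated through Month 6.

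- *Compound symmetry, ρ = 0.80.* Baseline: R² = 0.64. Six walks: R² = 6ρ²/(1 + 5ρ) = 3.84/5 = 0.768. Variance ratio 0.232/0.360 = 0.644, a reduction of 35.6%.
- *AR(1), r(0,6) = r(6,12) = 0.80, r(0,12) = 0.64.* Baseline: R² = 0.64² = 0.4096. Six walks: R² = 0.80² = 0.64. Ratio 0.360/0.5904 = 0.610, a reduction of 39.0%.
- *Intercept 0.6, AR 0.3, noise 0.1, with r(0,6) = 0.80 and r(0,12) = 0.73.* Reduction 31%.

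| Structure | SE as planned, 13 per arm | SE with common means |
|---|---|---|
| Compound symmetry | 20.0 m | 16.1 m |
| AR(1) | 25.6 m | 20.0 m |

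Range of the reduction:
- Compound symmetry, ρ from 0.60 to 0.90: 28% to 39%.
- AR(1), r(0,6) from 0.70 to 0.86: 33% to 42%.
- Mixed structures with r(0,6) = 0.80: 29% to 36%.
- With 2 of 15 dropping out per arm: 33% (compound symmetry) and 37% (AR(1)). These allow for the help that Course 1 data already give the planned model under dropout.

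**3. Covariance estimated.** Simulated ANCOVA of the Month 12 walk, 15 per arm, 5,000 runs; variance reduction relative to baseline alone:

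| Adjustment | Compound symmetry | AR(1) | Mixed |
|---|---|---|---|
| All six walks | 19% | 26% | 12% |
| Baseline plus Month 6 | 16% | 38% | 24% |
| Mean of the six walks | 34% | 23% | 27% |

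Runs at 13 per arm agree within a few points: about 11–23% for all six walks, and at most about 37% for the parsimonious forms. Six separate coefficients estimated from 26 to 30 patients use up much of the gain; one or two well-chosen ones keep most of it.

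**4. Illustrative power for 50 m, 13 per arm.** Covariance known: 67% to 85% (compound symmetry) and 46% to 67% (AR(1)). All six walks with estimated coefficients: 65% to 72% and 45% to 53%.

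**5. PVR and SF-36, compound symmetry, covariance known, assumed ρ of 0.5 to 0.8.**
- PVR: the schedule of assessments has hemodynamics at Months 0, 6 and 12, so R² = 2ρ²/(1 + ρ). At 0.5: 0.667/0.750, an 11% reduction. At 0.8: 0.289/0.360, a 20% reduction. SAP 5.1 also names hemodynamics at 3 and 9 months, which the schedule does not provide; I followed the schedule.
- SF-36: Months 0, 3, 6, 9 and 12, so R² = 3ρ²/(1 + 2ρ). At 0.5: 0.625/0.750, a 17% reduction. At 0.8: 0.262/0.360, a 27% reduction.

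**6. Months 1–4.** Pooled Arms 2 and 3 against Arm 1, relative to one pairwise contrast: (1/15 + 1/30)/(2/15) = 0.75, so 25% lower variance.

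**The case against.** The planned model is valid and unbiased, and constraining baseline alone is the standard approach that the SAP cites. The contrast is an unpowered secondary one, reported with a 95% interval and no multiplicity control. All of that stands, so this is a matter of efficiency only. Several stronger readings are tempting, and the documents do not support them.

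- **A reader might infer that a third of the information is simply thrown away.** That is the known-covariance case. The SAP estimates the covariance from a small sample and leaves its form open, and the Month 12 correlations are assumed. The realised gain could be as low as 11%.
- **A reader might infer that the constraint has no downside because randomisation guarantees it.** It does so under intent-to-treat. SAP 3.3 also plans a per-protocol set requiring at least three allocated Course 2 doses, which selects patients after the arms diverge, and an as-treated set grouped by treatment received. Equal Course 1 means are not assured in either set, and imposing them could bias the contrast. Common means would also alter the within-arm Month 6 to 12 estimates for objectives 2 and 3, which come from the same model.
- **A reader might take objective 1 as the only randomised test of a second course.** Objectives 5 and 9 also compare Arm 2 with Arm 3 at 12 months.
- **A reader might carry the 6MWD gain over to PVR and SF-36.** They have one and two pre-divergence values after baseline, not five, and the gain is smaller.
- **A reader might treat the power figures as a shortfall against plan.** SAP 2.4 sets 50 m for four doses against placebo; no target exists for eight doses against four.
- **A reader might call the Months 1–4 comparisons a defect.** They are labelled exploratory and the pairs are not named. The primary contrast already averages the two arms.

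**Conclusion.** The point holds as a loss of precision. In the intent-to-treat population, Arms 2 and 3 have equal expected 6MWD through the pre-dose Month 6 visit, and the Month 12 model uses that equality only at baseline. The available variance reduction for 6MWD is about 28–42% with known covariance, about 11–26% when all six walks are used with an unstructured covariance estimated from 26–30 patients, and about 16–37% with a parsimonious form, depending on the true correlation pattern. For PVR and SF-36 the known-covariance figures are about 11–20% and 17–27%.

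These rest on SD 85 m, a baseline to Month 6 correlation at or near 0.80, and assumed Month 12 correlations; for PVR and SF-36 every correlation is assumed. There is no bias, and the primary analysis is untouched. The change is worth making because the comparison is small, but it is a refinement of secondary analyses and not the repair of an invalid one.

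**What to change.** Before unblinding, amend SAP 5.2 as follows.

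1. In the intent-to-treat 12-month models for objectives 1, 5 and 9, give Arms 2 and 3 one common mean at each visit through pre-dose Month 6 and separate means afterwards. Name a parsimonious covariance structure in advance. Alternatively, adjust the Month 12 contrast for baseline plus Month 6, or for a fixed Course 1 summary such as the mean of the six walks.
2. State that the constraint is not applied in the per-protocol or as-treated analyses.
3. State whether the within-arm Month 6 to 12 estimates for objectives 2 and 3 come from the constrained model.
4. Optionally, report pooled Arms 2 and 3 against Arm 1 at Months 1–4 in the exploratory table.

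The cost is SAP wording (with matching text in Protocol 11.5) and a changed design matrix; no new visits or data are needed. The small downside is that the gain depends on the covariance form chosen, and shrinks if that form needs many estimated parameters.

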#### Analysis of the Durability of Primary Outcome (6MWD at 6 months)

To assess the durability of any improvement in 6MWD at 3 months vs. 9 months post last dose of cell therapy product (secondary objective 2), the repeated measures model up to month 12 will be used to estimate the least square mean difference from 6 months to 12 months within Arm 2 together with its 95% confidence interval, and used to test the hypothesis of no deterioration.

#### Analysis of the Incremental Effect of Delivery of 4 vs. 8 doses (6MWD from 6 to 12 months)

To estimate the incremental effect of delivery of 4 vs. 8 doses on the 6MWD (secondary objective 3), the repeated measures model up to month 12 will be used to estimate the least square mean difference from 6 months to 12 months within Arm 3 together with its 95% confidence interval.

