A phase 1 dose-ranging safety trial, Pulmonary Hypertension and Cell Therapy (PHACeT; ClinicalTrials.gov Identifier: NCT00469027), was performed using autologous EPC transiently transfected by electroporation with plasmid DNA containing the full coding sequence of human eNOS. This study enrolled 7 patients with a diagnosis of idiopathic PAH; 3 received a total of 7 million cells (Panel 1), 3 received 23 million cells (Panel 2) and one patient received 50 million

cells (Panel 3). Cells were delivered by central venous injection through the pacing port of a Swan-Ganz catheter with continuous monitoring of pulmonary arterial pressures in an intensive care environment. For added safety, the total cell dose delivered was divided into 3 aliquots and delivered over 3 days such that the initial "test" dose in Panel 1 was 1 million cells on day 1, followed by 3 million on days 2 and 3 (total of 7 million cells). Participants in Panel 2 received 3, 10 and 10 million cells (total of 23 million cells), and those in Panel 3 received 10, 20 and 20 million cells (total of 50 million cells), on days 1, 2 and 3 respectively. The primary safety analysis was change in pulmonary hemodynamic parameters before and 30 minutes after cell delivery. No deterioration in pulmonary hemodynamics was seen during cell delivery. Administration of 20 million cells as a single injection repeated on two consecutive days in Panel 3 and 23 million cells as a cumulative cell dose delivered over 3 days in Panel 2 were well tolerated. Moreover, there was a statistical trend towards improved total pulmonary resistance over the 3 day delivery period; although no sustained reduction in pulmonary arterial pressure or resistance was seen at 3 months. Of note, there were significant improvements in 6 minute walk distance (6MWD), which peaked at 1 month (~60 meters, p<0.01), persisting to 6 months (~40 meters, p<0.05). Quality of life measures (SF-36) and functional class were improved over the course of the study as well. Only one patient died during the study period.

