- Arm 1: Participants previously receiving placebo will now receive a course of 4 cell therapy treatments allowing all participants in this trial to have the opportunity to be given the active study product.
- Arm 2: Participants previously receiving EPCs will now receive the placebo study product to allow an assessment of the durability of any potential benefit of the cell therapy provided in Course 1 over the remaining 6 months of the study.
- Arm 3: Participants previously receiving EPCs will now receive a second course of cell therapy treatments, for a total of 8 doses of eNOS-transfected EPCs. This Arm will determine whether 8 repeated doses of the cell therapy product provides a greater incremental benefit than 4 doses.

After the 12-month treatment and follow-up period is complete, the study will be converted to a long-term follow-up registry extending to 10 years.

A detailed schematic of the study flow is found Appendix A.

4. Screening and Eligibility

Referrals for screening will be made by physicians who follow patients for clinical management of PAH at participating SAPPHIRE trial sites, all of which are specialized pulmonary hypertension clinics. Health records will be reviewed in compliance with the Federal Personal Information Protection and Electronic Documents Act (PIPEDA), provincial privacy laws, and local hospital privacy policies.

The research consent process will be initiated at the research site for potential participants who appear to be eligible based on available clinical information. For potential participants who wish to proceed with the trial and who provide written consent, research investigations will then commence. Screening investigations will be completed as outlined in the schedule of assessments in **Appendix B**.

4.1. Inclusion Criteria:

Patients participating in the study must meet ALL of the following inclusion criteria:

- Age \geq 18 years, \leq 80 years
- Established diagnosis of PAH due to the following:
 - o Idiopathic or heritable PAH;
 - o Scleroderma associated PAH (limited or diffuse);
 - o Drugs (anorexigens) or toxins;
 - o Congenital heart defects (atrial septal defects, ventricular septal defects, and patent ductus arteriosus) repaired ≥ 1 years

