**Secondary objectives:**

1. To compare the sustained effect of delivery of 4 vs. 8 doses of the cell therapy product on 6MWD at 12 months (i.e. Arm 2 vs. Arm 3)
2. To assess durability of any improvement in 6MWD at 3 vs. 9 months post last dose of cell therapy product (Arm 2 only)
3. To determine the incremental effect of delivery of 8 vs. 4 doses of the cell therapy product on 6MWD at 6 and 12 months (Arm 3 only)
4. To assess the cumulative effect of 4 doses of the cell therapy product on pulmonary vascular resistance at 6 months (Arms 2 and 3 vs. Arm 1)
5. To compare the sustained effect of delivery of 4 vs. 8 doses of the cell therapy product on pulmonary vascular resistance at 12 months (i.e. Arm 2 vs. Arm 3)
6. To assess durability of any improvement in pulmonary vascular resistance at 3 vs. 9 months post last dose of cell therapy product (Arm 2 only)
7. To determine the incremental effect of delivery of 8 vs. 4 doses of the cell therapy product on pulmonary vascular resistance at 6 and 12 months (Arm 3 only)
8. To assess effect of cell therapy on Quality of Life measured by the SF-36 at 6 months (Arms 2 and 3 vs. Arm 1)
9. To compare the sustained effect of delivery of 4 vs. 8 doses of the cell therapy product on Quality of Life measured by the SF-36 at 12 months (i.e. Arm 2 vs. Arm 3)
10. To assess the effect of cell therapy on a combined endpoint of death, or clinical worsening of pulmonary arterial hypertension at 6 and 12 months
11. To assess effect of cell therapy on measures of RV function by echocardiography at 6 and 12 months
12. To assess effect of cell therapy on RV function by Magnetic Resonance Imaging (MRI) at sites where this is available in patients with no contraindications for MRI (i.e. prostacyclin infusion pump, claustrophobia) at 6 and 12 months

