***The primary effect measure is at the 6 month time point.***

However, the study continues beyond 6 months in order to address a number of important secondary endpoints. ***Importantly, the blind will continue over the entire 12 month period of the study.***

- **Course 2:** In the second 6 month period, the study treatments will be altered to address specific questions about the timing and durability of this cell therapy:
  - Arm 1: Participants previously receiving placebo will now receive a course of 4 cell therapy treatments allowing all participants in this trial to have the opportunity to be given the active study product.

- Arm 2: Participants previously receiving EPCs will now receive the placebo study product to allow an assessment of the durability of any potential benefit of the cell therapy provided in Course 1 over the remaining 6 months of the study.
- Arm 3: Participants previously receiving EPCs will now receive a second course of cell therapy treatments, for a total of 8 doses of eNOS-transfected EPCs. This Arm will determine whether 8 repeated doses of the cell therapy product provides a greater incremental benefit than 4 doses.

After the 12-month treatment and follow-up period is complete, the study will be converted to a long-term follow-up registry extending to 10 years.

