- Must have a resting arterial oxygen saturation (SaO2)  $\geq$  88% with or without supplemental oxygen as measured by pulse oximetry at the Screening Visit
- Must not be enrolled in an exercise training program for pulmonary rehabilitation within 3 months prior to the Screening Visit and must agree not to enroll in an exercise training program for pulmonary rehabilitation during the Screening Period and the first 6 months of the study. Participants enrolled in an exercise program for pulmonary rehabilitation 3 months prior to screening may enter the study if they agree to maintain their current level of rehabilitation for the first 6 months of the study
- Women of child-bearing potential (defined as less than 1 year post-menopausal and not surgically sterile) must be practicing abstinence or using two highly effective methods of contraception (defined as a method of birth control that results in a low failure rate, i.e., less than 1% per year, such as approved hormonal contraceptives, barrier methods [such as a condom or diaphragm] used with a spermicide, or an intrauterine device). Subjects must have a negative  $\beta$ -hCG pregnancy test during the Screening period and negative urine pregnancy test results at all other study visits
- Must be willing and able to comply with study requirements and restrictions.

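### The 8 versus 4 dose effect in secondary objective 3 is an uncontrolled Month 6-to-12 change within Arm 3, and the randomized Arm 3 vs Arm 1 contrast at Month 12 is not planned

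*SAP*

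**What the plan says.** Secondary objective 3 (Protocol 2.2; SAP Objectives) concerns the incremental effect of 8 versus 4 doses "on 6MWD at 6 and 12 months (Arm 3 only"). In SAP 5.2 and Protocol 11.7 its only analysis is a single-arm change from the model fitted up to Month 12, "used to estimate the least square mean difference from 6 months to 12 months within Arm 3 together with its 95% confidence interval". The Course 2 rationale gives Arm 3 a causal role: "This Arm will determine whether 8 repeated doses of the cell therapy product provides a greater incremental benefit than 4 doses" (SAP 2.1; Protocol 3).

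At Month 12 the only between-arm 6MWD comparison named is under objective 1, where the model is used to "estimate the adjusted least square mean difference between Arm 2 and Arm 3 at 12 months" (SAP 5.2; Protocol 11.5). Further pairwise comparisons are listed for Months 1 to 4 and Months 7 to 10, without saying which pairs. Arm 1 enters a 12-month comparison by name only in the three-arm log-rank test of the combined endpoint.

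On dosing, Protocol Appendix H states: "Delivery of the study product to participants will take place at the following visits: Months 0-3 and Months 6-9". In Course 2, Arm 1 crosses to active product: "Participants previously receiving placebo will now receive a course of 4 cell therapy treatments" (Protocol 3).

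**The concern.** A claim about 8 versus 4 doses rests on a change with no comparator, in a trial that has two concurrent randomized arms to compare with. Whatever else moves 6MWD between Months 6 and 12 is counted as effect of the second course.

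The documents give reasons to expect movement in either direction. The Background section describes PAH as progressive. Protocol 7.8 permits all PAH-specific drugs throughout. The restriction on joining a rehabilitation programme applies only "during the Screening Period and the first 6 months of the study" (SAP 4.1; Protocol 4.1), so it lapses when the measured interval begins.

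Following the plan exactly could therefore report a benefit of the second course that does not exist, or hide one that does. The contrast that best matches the stated question is available from the same model but is not specified.

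**Working it through.** **Inputs.** SD 85 m, baseline-to-Month-6 correlation 0.80, 13 evaluable and 15 randomized per arm, two-sided 5% (SAP 2.3; Protocol 11.1). The documents give no Month 6-to-12 correlation and no trend. I carry 0.80 forward, vary it from 0.70 to 0.90, and assume trends of 20 m and 30 m.

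**The plan's own figure.** Residual SD = 85 × √(1 − 0.80²) = 51 m. For the average of Arms 2 and 3 vs Arm 1, SE = 51 × √(1/13 + 1/26) = 17.3 m. Power for 50 m on 35 df is 80.1%, against the stated 80%, so it reproduces. It concerns only the Month 6 primary contrast.

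**Status at Month 12, from the dosing months**

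| Arm | Active doses | Last active dose | Months since |
|---|---|---|---|
| 1 | 4 | Month 9 | 3 |
| 2 | 4 | Month 3 | 9 |
| 3 | 8 | Month 9 | 3 |

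At Month 6, Arm 3 had received 4 doses, the last at Month 3, so it was also 3 months past its last dose.

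**What each quantity estimates.** Let R be the mean 6MWD at Month 6 after an active Course 1. Define:
- I: extra response to 8 versus 4 doses at equal time since last dose
- T: calendar trend over Months 6 to 12, common to all arms
- W: waning of the Course 1 response from 3 to 9 months after its last dose
- D: loss from starting treatment 6 months later

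Month 12 means are R + I + T (Arm 3), R − W + T (Arm 2) and R − D + T (Arm 1). Hence:
- Arm 3 change, Month 6 to 12 = **I + T**
- Arm 3 minus Arm 2 at Month 12 = **I + W**
- Arm 3 minus Arm 1 at Month 12 = **I + D**

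**Behaviour.** Simulation with 20,000 trials per setting, compound symmetry with correlation 0.80, and a three-arm baseline-adjusted model at Month 12. Entries are the mean in metres, with the share of 95% intervals excluding zero for n = 13 / 15. Terms not shown are zero.

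| Setting | Arm 3 change | Arm 3 − Arm 2 | Arm 3 − Arm 1 |
|---|---|---|---|
| T = −30 | −30 (47% / 52%) | 0 (5%) | 0 (5%) |
| T = +30 | +30 (46% / 52%) | 0 (5%) | 0 (5%) |
| I = 30, T = −30 | 0 (5%) | +30 (30% / 34%) | +30 (30% / 34%) |
| W = 20 | 0 (5%) | +20 (16% / 18%) | 0 (5%) |
| D = 20 | 0 (5%) | 0 (5%) | +20 (16% / 18%) |

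The W = 20 row is prompted by the phase 1 6MWD gains, "which peaked at 1 month (~60 meters, p<0.01), persisting to 6 months (~40 meters, p<0.05"), a fall of about 20 m. It shows that Arm 3 vs Arm 2 alone could present maintenance as added benefit.

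**Analytic check of the within-arm interval.** SD of change = 85 × √(2 × (1 − 0.80)) = 53.8 m. SE = 53.8/√13 = 14.9 m or 53.8/√15 = 13.9 m. Probability that the 95% interval excludes zero when I = 0 (noncentral t, n − 1 df):

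| Trend | n = 13 | n = 15 | Range, correlation 0.70-0.90 |
|---|---|---|---|
| 20 m | 23.5% | 26.9% | 17-48% |
| 30 m | 45.7% | 52.1% | 33-81% |

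These are paired-t approximations to the planned REML model. With pooled df of 3(n − 1) = 36 or 42, the figures are 26-29% and 50-56%.

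**Precision of the randomized contrasts.** SE = 85 × √(1 − r²) × √(2/n), where r is the baseline-to-Month-12 correlation:
- r = 0.80: SE 20.0 m (n = 13) or 18.6 m (n = 15); power for 30 m is 31% or 35%.
- r = 0.64: SE 25.6 m or 23.8 m; power 21% or 23%.
- As a difference in Month 6-to-12 change (correlation 0.80), Arm 3 minus Arm 2 has SE 53.8 × √(2/n) = 21.1 m or 19.6 m; power 28% or 32%.

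**The case against.** The best defence is that a randomized 4 versus 8 dose comparison is already planned under objective 1, and that objective 3 is openly limited to Arm 3 and calls for an estimate with an interval, not a test. Both are true, so nothing is concealed. But the Arm 2 vs Arm 3 contrast estimates I + W, and its presence does not make I + T an incremental effect. An interval offered as the effect of 8 versus 4 doses will be read against zero whether or not a test is named. Setting the Arm 2 and Arm 3 changes side by side removes a common trend, but it again leaves I + W.

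The comparisons at Months 7 to 10 could include Arm 3 vs Arm 1 at Month 10, when both arms are one month past their last active dose. That reading is possible, but the pairs are not listed and Month 12 is still not covered.

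The sizes rest on assumed trends. At 10 m the interval excludes zero in only about 10% of trials. The 5% for the randomized contrasts requires W or D to be zero and the trend to be the same in every arm; added PAH drugs could differ by arm. The 20 m used for waning comes from 7 phase 1 patients, over months 1 to 6 after a single three-day delivery, and is itself uncontrolled. It illustrates the mechanism and is not an estimate of W here.

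Neither randomized contrast isolates I, and both are imprecise. That stands. It calls for accurate labels on both contrasts, and it does not make the uncontrolled change a dose effect.

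**Conclusion.** The concern holds. The Arm 3 change estimates increment plus trend, and this follows from the dosing schedule whatever the size of the trend. How often it would mislead depends on the trend: about a quarter of trials at 20 m and about half at 30 m, assuming SD 85 m, correlation 0.80, 13 to 15 per arm and no true increment. An opposite trend can mask a real increment just as easily.

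The fault lies in the label and the choice of estimate for one secondary objective. It should be corrected, but it does not touch the primary analysis. Confidence is high on the structure; the percentages are only as good as the assumed trends.

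**What to change.** Before unblinding:

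1. In SAP 5.2 and Protocol 11.7, replace the objective 3 analysis with text such as:

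   > The Month 6-to-12 change within Arm 3 will be reported descriptively. Inference about the second course will use two randomized contrasts at Month 12 from the 12-month model, each with a 95% CI: (a) Arm 3 vs Arm 2, the effect of a second course versus placebo in Course 2, noting that time since last active dose differs (3 vs 9 months); (b) Arm 3 vs Arm 1, 8 vs 4 doses at equal calendar time and equal time since last dose, noting that Arm 1 received its doses later in the disease course.

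2. Give contrast (a) the same description under the Month 12 analysis (SAP 5.2; Protocol 11.5).
3. Amend the Arm 3 restriction in objective 3 (Protocol 2.2; SAP Objectives), and in objective 7 (PVR) if it is to be analysed the same way. Reword the Course 2 rationale for Arm 3 (Protocol 3; SAP 2.1) to refer to its comparison with Arms 1 and 2.

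**Cost.** One extra contrast from a model already planned, no new data, and matching text edits. At correlation 0.80 the SE rises from 13.9-14.9 m within Arm 3 to 18.6-20.0 m, so these are estimates with intervals and not powered tests. Contrast (b) still carries the delayed-start term, and it adds one more secondary comparison without multiplicity adjustment under SAP 3.1.
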